In contradistinction, the studies by Worda et al⁸ and Connor et al.^{16-21,26,31} have examined topical eyelid androgen application with generally favorable effects on tear film parameters and also a good safety profile. However, the eyelid application studies were not consistent in the subject type (e.g., both males and females were not uniformly enrolled), the androgen status and serum levels were not assessed prior to, or following androgen application and the studies were only published as peer-reviewed abstracts and mostly were done in one laboratory. This prospective randomized, controlled double masked study aims to evaluate the efficacy and safety of topical transdermal application to the eyelids of low dosage androgen in a population of patients with evaporative dry eye associated with meibomian gland dystrophy and aqueous tear deficient dry eye.

Methods

Study objective

To evaluate the safety and efficacy of an FDA-approved androgen nasal supplement (Natesto, Acerus Pharmaceuticals Corporation, 4.5% gel concentration) in males and females with dry eye of either aqueous tear deficiency or evaporative subtype.

Clinical hypothesis

- Natesto applied to upper and lower eyelid skin is more effective than placebo as measured by fluorescein tear breakup time (TBUT) and mean scores for meibomian secretion quality at 4 weeks and overall ocular comfort at 8 weeks.
- Natesto has an acceptable safety profile in ocular structures and general systemic system.

Statistical Hypotheses:

H₀: There is no difference in change from baseline to week four for either fluorescein breakup time (TBUT) or meibomian secretion score (0 - 24 scale) between the test and placebo-treated sample.

 H_A : There is a difference in the change from baseline to week four for either fluorescein breakup time (TBUT) or meibomian secretion score (0 – 24 scale) between the test and placebo-treated sample

Overall study design

Structure

We propose a randomized controlled trial (RCT) of one month duration dosing BID with

an FDA-approved androgen nasal supplement (Natesto, Acerus Pharmaceuticals

Corporation, 4.5% gel concentration) in males and females with dry eye of either aqueous tear deficiency or evaporative subtype.

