The test formulation will be marketed Natesto gel, containing 5.5 mg testosterone per pump (17 β -Hydroxyandrost-4-en-3-one; inactive ingredients are castor oil, oleoyl polyoxylglycerides and colloidal silicone dioxide; Natesto package insert). The placebo is the exact same formulation without 17 β -Hydroxyandrost-4-en-3-one. The drug and placebo will be delivered to and dispensed by Caduceus Medical group in Yorba Linda for MBKU's study use.

Dosage regimen

One dose per eyelid of masked gel, which is one pump from the dispenser, represents 5.5 mg for each eyelid, will be applied on the surface of upper and lower eyelid skin each eye twice per day (separated by 8 hours) for a total daily dose of 22mg.

Duration

2-week screening period; 4-week masked treatment phase, 8-week washout phase.

Overall study duration 14 weeks

Visit schedule (see Table 4 and 5)

- Visit 1: Screening visit (Day -14)
- Visit 2: Baseline (Day 0) : the drug (placebo) is prescribed and dispensed.
 Instructions are given on how to properly apply the drug. Subjects are instructed to keep the container even if the drug is finished. All containers need to be checked in the following two visits (visit 3 & 4)
- Visit 2a: serum blood draw for baseline total testosterone level, hematocrit, lipid panel, PSA for men only at clinical laboratory

- Visit 3: Two-week visit: check the drug (placebo) to see if supplement needed.
 Empty containers need to be collected.
- Visit 4: Week 4: the drug (placebo) is discontinued. All dispensed containers need to be collected.
- Visit 4a: serum blood draw for treatment period total testosterone level at clinical laboratory (must be in AM, and must be within two hours of application)
- Visit 5: Week 8: 4-weeks washout phase follow up
- Visit 6: Week 12: 8-week washout phase follow up

Evaluation criteria

Efficacy measures

Primary

- Fluorescein tear breakup time (FTBUT)
- MGD secretion grade (0-24 scale)

Secondary:

- 1. Schein Questionnaire and Ocular Surface Disease Index (OSDI)
- Corneal and conjunctival staining as per the Oxford and National Eye Institute (NEI) schemes
- Tear Meniscus Height (TMH) utilizing Keratography 5M (K5M Oculus, Inc Arlington,WA)
- 4. Eyelid signs grading of orifice metaplasia, vascularity, plugged orifice, lid margin irregularity, ridging between orifices, and antero-posterior orifice displacement
- 5. Meiboscore utilizing K5M
- 6. Schirmer I test without anesthetic

Exploratory:

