Due to the relatively small sample size (n < 200) and the need to control and balance the influence of covariates, such as age and sex, we adopted the method of covariate adaptive randomization.⁴⁵ With two covariates of sex (2 levels: male, female) and age (2 levels: <50, >50) between study arms (treatment and control), a total of 4 block combinations is produced. After a participant has passed the screening and day 0 examinations, the first 10 participants will be assigned to one of the treatment groups within each block by simple randomization, according to a randomization scheme ([name] [name] will generate this). The next new participant is then sequentially assigned to a particular treatment group by considering the specific covariates and previous assignments of participants. For example, the first 10 participants assignment are broken down by covariates as in Table 3. Then the 11^{th} participant, who is male and >50 years old, needs to be assigned to a group (control vs. treatment). Based on the characteristics of the 11th participant, the method adds marginal totals of the corresponding covariate categories for each group and compares the totals. The participant is assigned to the group with the lower covariate total to minimize imbalance. In this example, the appropriate categories are male and > 50 years old, which results in a total of 6 (3 for male and 3 for >50) for the control group and a total of 5 (3 for male and 2 for >50) for the

treatment group. Because the sum of marginal totals is lower in treatment group

(5<6), the 11th participant is assigned to the treatment group.

Control group		Sex	Marginal total	
		Male	Female	
Age	<50	2	0	2
	>50	1	2	3
Marginal total		3	2	5

Table 3. Procedure of randomization

Treatment group		Sex	Marginal total	
		Male	Female	
Age	<50	1	2	3
	>50	2	0	2
Marginal total		3	2	5

Every participant is assigned a number from 001 to 100 and recorded with the specific number during the whole study until de-identified at the end of the study.

Masking

- 1. The participants will be masked from the assignment of the treatment group.
- An unmasked research assistant will recruit and schedule subjects and administer the questionnaires and exclude subjects based on the above-mentioned inclusion and exclusion criteria.
- 3. Another unmasked research assistant will implement the randomization based on the above covariate adaptive randomization method.

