5. Subjects are required to refrain from using any eye drops or artificial tears for a minimum of 12 hours prior to their visit and dilation drops within 1 week prior to their visit. Subjects will be asked to refrain from any eye rubbing, eye makeup, or facial products (e.g., creams, lotions) near the eyes on the day of the study. Table 5 shows the schedule for all the visits and procedures

Table 4: Procedure summary

Ducardura	Notos
Procedure	Notes
Informed Consent / HIPAA	
Medical/CL History	
Visual Acuity	
Questionnaires: OSDI, Schein	Survey results masked from examining clinician
Biomicroscopy – lid signs (0 – 5 scale)	Plugging, notching, ridging, teleangiectasia, metaplasia
Tear osmolarity	Tearlab; take higher of R, L values
NIBUT (Oculus Keratograph)	3 blinks, hold, average 3 values each eye
[5 minute rest period to stabilize tear film]	
Tear meniscus height (Oculus Keratograph)	< 0.2 mm; not specified by DEWS II
TBUT ^{a,} seconds (fluorescein; nearest 1/10 th)\	Mean, median of 3 measurements; alternate eyes; 30 sec. rest periods
Corneal Staining ^a : Both OSS (0 – 12 system) and NEI (1995) scale (0 – 33) for cornea, conjunctiva	OSS (SICCA group): 0 – 6 for cornea, 0 – 3 for nasal, temporal conjunctiva) NEI: 0 – 3 score for each of 5 zones on cornea (0 – 15), 6 zones for conj. (0 – 18); Total Scale 0 – 33.
Conjunctival Staining ^{b,}	OSS (SICCA group): 0 – 3 for nasal, temporal conjunctiva (0 – 6 total)) NEI: six-zone system. 0 – 3 per zone; 0 – 18 per eye
Total Staining, for Severity Purposes:	 OSS: 0 − 12; if cornea > 5 spots, and conjunctiva > 9 spots = dry eye NEI: 0 − 15 + 0 − 18 = 0 − 33 maximum
Meibomian Gland Excreta Grading (DEWS II/MGD workshop): lower eyelid (central 8 glands); 0 – 3 scale ^c	Q-tip or MGE
Gland Imaging:	LipiView II or Keratograph 5M;
	meiboscore in 0.5 scale increments; % gland area present
Schirmer I sans anesthetic; 5 mins	Move strip at 2 mins if no wetting ⁴⁶
Sentimer i sans ancouncue, 5 mills	move surp at 2 mins it no wetting

^a 2.0 μL of 1% NaFI (micropipette); measure TBUT, then both OSS and NEI within 4 minutes
 ^b Lissamine green (strips; wet once, shake off excess; measue within 2 minutes due to elution of dye)

c Bron et al., 1991 and Bron and Foulks, 2003, scale: 0 = clear; 1 = cloudy; 2 -= cloudy with particles, 3 = inspissated/toothpaste

Procedure	Screening	0 Week Baseline (Day 0)	2 Weeks	4 Weeks	8 Weeks (4 Weeks washout)	12 Weeks (8 Weeks washout)

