- Ocular Surface Disease Index (OSDI);^{49,50} a score of ≥13 out of 100 indicates dry eye
 - Subjects will be asked to fill out the questionnaires prior to reporting for the study. The questionnaires will not be scored until after data capture was completed on the subject.
- Tear meniscus height (OD/OS): Measured using Oculus Keratograph 5M: cursor measurement of three lower meniscus heights at approximately 7:00, 6:00 and 5:00
- Tear osmolarity using the Tear Lab method

- Slit Lamp Examination of the health of anterior structures (OD/OS):
 - Upper and lower lids and lashes assessed utilizing white light, diffuse beam (14 mm round), low illumination and 10x magnification
 - Bulbar and palpebral conjunctiva were then assessed using the same settings as those used for lids
 - Corneal health will be assessed utilizing white light parallel parallelepiped beam (~2mm wide, 14 mm tall) at a medium illumination and 16x magnification.
- Eyelid sign grading (OD/OS): Each of the following signs was given a grade of 0 (absent) or 1 (present). A grade of 1 was given if a feature had 2 or more appearances along the lid margin for that eye: ⁵¹⁻⁵³
 - Orifice metaplasia.
 - Orifice metaplasia: Clear-white filamentous shafts at the gland orifice, evident on direct illumination.
 - Vascularity/ brush marks.
 - Telangiectasia coming from palpebral conjunctiva.
 - Plugged or capped orifices (present if more than one caps on a given eyelid).
 - Ridging between orifices.
 - Eyelid margin irregularity.
 - Notching, ridging at the posterior lid margin border. [these two are equivalent]
 - Anterior or posterior orifice displacement.

- Tear Break Up Time (TBUT) with fluorescein staining (OD/OS): Detailed procedure description below.
- Corneal staining with sodium fluorescein (OD/OS)
- Staining was assessed as per the NEI (Score of 0-15) and OSS (screening and baseline only) schemes for each eye;⁵⁴⁻⁵⁶ detailed procedure description below.
- Conjunctival Staining with lissamine green (OD/OS):
- Staining was assessed as per the NEI (Score of 0-18) and OSS(Score of 0-12) schemes for each eye; ⁵⁴⁻⁵⁶ detailed procedure description below.
- Secretion Quality (OD/OS):
- Meibomian gland secretion quality will be assessed according to the Bron scale^{6,57} utilizing a Meibomian Gland Evaluator (MGE)⁵⁸ in order to standardize pressure applied and therefore values measured (gentle rather than a forceful expression);detailed procedure below.

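### The plan does not settle whether an unmasked assistant handles OSDI and Schein after baseline or subjects complete the forms alone, and it does not say that the scorer is masked

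*Combined protocol and SAP*

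**What the plan says.** - **Masking, item 1:** "The participants will be masked from the assignment of the treatment group".
- **Masking, item 2:** "An unmasked research assistant will recruit and schedule subjects and administer the questionnaires"; the same assistant also excludes subjects on the eligibility criteria.
- **Masking, item 3:** a second person takes the assignment step: "Another unmasked research assistant will implement the randomization".
- **Masking, item 4:** the principal investigator is masked at the follow-up dry eye evaluations. No item covers whoever collects or scores the symptom forms.
- **Procedure II (Dry Eye Work-up):** "Subjects will be asked to fill out the questionnaires prior to reporting for the study". Scoring waits until data capture on the subject is finished. The scorer is not named.
- **Table 4:** the note on the questionnaires reads "Survey results masked from examining clinician".
- **Table 5:** the questionnaires are scheduled at screening, baseline and weeks 2, 4, 8 and 12.
- **Evaluation criteria:** Schein and OSDI are item 1 of the secondary efficacy measures. The clinical hypothesis also refers to "overall ocular comfort at 8 weeks".
- **Appendix II:** both instruments are fixed-choice tick-box forms. The OSDI formula is printed, and not-applicable items are left out of the denominator.

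**The concern.** OSDI and Schein are subjective. If the person who hands out the forms, answers questions about them or scores them knows the arm, that knowledge can reach the recorded score even though the subject is masked. The existing safeguards point elsewhere. Item 4 masks the investigator, who is not the person named for the questionnaires. Table 4 keeps the answers from the examiner, which protects the examination from the symptom scores but does not protect the symptom scores from knowledge of the arm.

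The between-arm comparison on a secondary symptom measure is at stake, along with the trial's description of itself as double masked. This is separate from the same assistant's role in enrolment. Making the next assignment harder to predict would not change who handles the forms after randomisation.

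**Working it through.** The plan gives no effect size, SD or power for a symptom score, so it has no figure on this point to reproduce. The check is mainly a comparison of sections.

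**1. The two descriptions side by side**

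- *Who is involved:* Masking item 2 names an unmasked assistant who administers. Procedure II names the subject, who fills in the form.
- *When:* item 2 gives no visit. Procedure II says before the subject reports for the study and sits in the enrolment work-up. Table 5 gives timing for six visits but no personnel.
- *Who scores:* item 2 is silent. Procedure II delays scoring but names no one.

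Baseline is day 0 and treatment starts there, so 6 − 2 = 4 visits fall after assignment. For those four visits neither description is stated to apply.

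**2. Does this assistant need to know the arm?**

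The stated duties are recruiting, scheduling, questionnaires and exclusion. Item 3 gives the assignment to a different assistant, and the section on the test formulation has an outside medical group dispense the product. No stated duty of this assistant needs the allocation.

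**3. What the scales do (properties of the forms, not estimates of bias)**

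- OSDI = sum × 100 / (items answered × 4). With all 12 answered, one category on one item is 100/48 = 2.1 points, two are 200/48 = 4.2, and five are 500/48 = 10.4.
- Schein: six items scored 0–4, maximum 24. One category on one item is 1 point.
- Items 6 to 12 of the OSDI, seven of the 12, offer a not-applicable response. Example with an assumed sum of 12: 12 × 100/48 = 25.0 with all items answered. If one item scored 0 is treated as not applicable, the score is 12 × 100/44 = 27.3. Handling of these items therefore changes the score.

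**4. Illustration of what a bias would do**

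The documents give no size for such a bias, so the range 0 to 0.5 SD is an assumption. So is the use of a two-sided t-test at 0.05, which is the test behind Table 2; the analysis section lists other tests. With 17 per arm, df = 32, noncentrality = b × √(17/2) and no true effect, the chance of a significant result in the direction of the bias is:

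- b = 0: 2.5%
- b = 0.1 SD: 4.7%
- b = 0.2 SD: 8.2%
- b = 0.3 SD: 13.3%
- b = 0.5 SD: 29.3%

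The same figures apply whichever arm the bias favours.

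**5. Effect on the design figures**

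The noncentral t calculation for break-up time (difference 2.5 s, SD 2.5 s, 17 per arm) gives 0.80704, against 0.807037 in Table 2. Nothing in this point changes that figure.

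**The case against.** The strongest reply is that administering may mean no more than handing out and collecting. Procedure II has the subject fill in the form, Appendix II is a tick-box form addressed to the subject, and the OSDI formula is printed. No section describes an interview, prompting or an assistant writing down answers. Item 2 can also be read as a screening duty. Questionnaires stand there next to recruitment and exclusion, and OSDI and Schein thresholds are themselves entry criteria, applied before any arm exists. On that reading the two sections do not conflict.

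Much of this stands. Masked subjects ticking fixed responses leave an assistant limited room to influence the answers. A reader might infer that the symptom comparison is biased toward the active gel. The documents do not support that, because neither the occurrence nor the direction of a bias is established. A reader might also take the 4.2- and 10.4-point figures as a plausible distortion. They are not: a 10.4-point between-arm shift would need an average of five categories per subject, all in one direction, in one arm relative to the other. Nor does first place in the secondary list confer any stated priority. The clinical hypothesis does not say which instrument measures ocular comfort, and Table 5 also lists an MGD-specific questionnaire.

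The reply does not close the gap. The benign reading has to be supplied by the reader. Item 2 is not limited to screening, Procedure II does not mention follow-up visits, and neither says that the scorer is masked. Explanations of items, cues during contact with the subject, and handling of not-applicable items remain possible routes.

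**Conclusion.** The point holds as an unresolved inconsistency in how two secondary measures are collected, with an avoidable opening for bias. The documents allow someone who knows the arm to handle, explain or score OSDI and Schein at four post-baseline visits. They do not show that this will happen or which way it would act, and its size cannot be derived from them. The percentages in the illustration rest on an assumed range.

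It would be wrong to read this as a threat to the main result. Break-up time and secretion grade are the primary measures and the only variables in the statistical hypotheses, and this route does not reach them. If unaided self-completion is already intended at every visit, the remaining risk is small. The change is still worth making, because it replaces a stated rule that conflicts with double masking and costs little.

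**What to change.** Reconcile Masking item 2 with Procedure II:

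- State that subjects complete OSDI and Schein themselves, without assistance, at every visit in Table 5.
- State that the assistant who handles and scores the forms has no access to the allocation, and drop the description of that assistant as unmasked.
- State that scoring, including not-applicable items, follows the printed formula and is finished before unmasking.

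**Cost:** wording in two sections. No extra staff is needed, because the second assistant already implements the randomisation. The downside is administrative: allocation records must be kept from the first assistant. That should include the running covariate totals, because after the first 10 participants the arm follows from those totals and the subject's sex and age, which a recruiting assistant knows. Sample size, power and the primary analysis stay as they are.

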- Comparison of National eye Institute (NEI) to Ocular Staining Score (OSS) (DEWS II recommendation) staining scheme for efficiency
- 2. Repeatability of the above two staining schemes and meibomian gland secretion scores

Pharmacokinetic measures

• The patients will have blood samples (20 ml) drawn for the determination of total serum testosterone. Blood will be drawn at baseline and within two hours of dose application at Week 4 visit.

Safety measures

- Adverse events (treatment related and treatment unrelated)
- Visual acuity (BCVA ETDRS)
- Biomicroscopy
- Ophthalmoscopy exam
- IOP
- Male scalp hair evaluation
- Female hair evaluation (upper lip, chin, cheeks, scalp)

Subjects

Subjects will consist of a convenience sample of patients over 18 years old with signs and symptoms of dry eye disease (DED). Moderate to severe dry eye subjects who have either aqueous tear deficiency or evaporative dry eye related to meibomian gland

dysfunction will be recruited. The diagnosis of DED is made according to the DEWS II diagnostic criteria based on:

- 1. DE symptomatology: OSDI score \geq 13 and Modified Schein score \geq 7.5
- 2. Plus one of the following:
 - a. NIBUT < 10 seconds or fluorescein breakup time ≤ 6.0 seconds or
 - b. Osmolarity \geq 308 mosm/L in either eye or intraocular difference > 8 mosm/L or
 - Ocular surface staining (SICCA scale) > 5 corneal spots, > 9 conjunctival spots
 - d. Conjunctival-corneal epithelial damage (fluorescein, rose bengal, or lissamine green staining score >3 points).
- 3. Subtype Tests: severity according to the DEWS II Dx report;⁴ page 556
 - a. Aqueous tear deficiency: non-invasive meniscus height (TMH) ≤ 0.2 mm
 - b. Evaporative: only moderate to severe included:
 - Moderate: 1) orifice plugging, 2) lid margin vascularity, 3) gland secretion grade 8 – 12 (central 8 glands, 0 – 3 scale each),
 4) expressibility grade 2
 - Severe: 1) lid margin dropout or displacement, 2) gland secretion score ≥ 13, 3) expressibility grade of 3

The subjects will be recruited from among students, staff, faculty and patients from Ketchum Health, the clinical facility at Marshall B. Ketchum University. Additionally, the study will be advertised on social media to maximize the recruitment pool, such as Facebook, Instagram, and Twitter. Subjects will be sex-, and age-matched as they are enrolled since these parameters affect dry eye parameters such as marginal changes and meibomian gland secretion. ⁴⁴

Sample size estimation

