- 4. The principal investigator is masked from tests and placebo formulation during the follow up dry eye evaluations on subjects.
- 5. All masked information will only be opened at the end of the study or unless an adverse event (AE) requires unmasking to determine whether the AE was due to the treatment medication.

Study Sites

 Southern California College of Optometry at Main Campus ([name]). Main site for dry eye examination

Inclusion & Exclusion Criteria

Inclusion criteria

There are no restrictions for subject inclusion based on ethnicity, race, or occupation. All subjects meet the following criteria:

- 1. Male or female age over 18
- 2. Able and willing to follow study instructions.
- 3. Are able to provide written informed consent
- 4. Written authorization for use or release of health and research study information will be obtained
- Are willing to discontinue use of artificial tears and makeup on the study visit days
- 6. Able and willing to attend the clinical laboratory for morning blood draws to assay serum testosterone in addition PSA levels for men.
- 7. Patient must have a best corrected visual acuity of 20/40 or better in each eye
- 8. Patients must have normal lid position and closure

- Patients' willingness and ability to cooperate with the investigator and follow all instructions
- 10. A negative urine pregnancy test result for women of childbearing potential
- 11. Women of childbearing potential (from 18 to 50 years old) must have a history of bilateral tubal ligation or use contraceptives, implants, injectables, transdermal patch or IUD for birth control during the study. Patients taking oral contraceptives must not miss 2 or more doses in a one-month period. If these methods of birth control do not apply, women of childbearing potential must have a monogamous partner who has had a vasectomy at least 3 months before the screening visit. The date of the vasectomy and physician contact information must be documented in the source documents.
- 12. Subjects must have a meibomian gland secretion score of 8 or greater (0 24 scale).
- 13. Subject s must have at least 50% meibomian glands present in the upper eyelids.

Exclusion criteria

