Appendix III: Dry Eye Classification Criteria and Appendix V: Staging the Severity of MGD-Related Ocular Surface Disease

17. General statistical methods and types of analyses

- Comparisons, ANOVA, meibomian secretion scores, meibomian gland dropouts, OSDI
- The primary visit is week 4 and primary efficacy variables are the FTBUT and quality of meibomian secretions
- A two-sided test with p-value less than or equal to 0.05 will be considered as statistically significant.
- 18. Comparisons between pairs of treatment groups will be done with Cochran-Mantel Haenszel (CMH) tests, stratified by the ocular discomfort strata. Within Strata comparisons will be done with Wilcoxon rank-sum tests for both ordinal and continuous variables. For nominal variables, within strata comparisons will be done with Pearson's chi-square or Fisher's exact tests.
- 19. Exploratory pharmacokinetics data analysis
- Summary statistics of testosterone, dihydrosterosterone, and 3-alphaandrostanediol glucuronide serum concentrations will be calculated. The relationships between treatment time and gender will be examined.

Confidentiality

The identity of the subjects will be treated as confidential. The results of the study, including any other data, may be published for scientific purposes but will not reveal the name of the subject or include any identifiable references to the subject. Although

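### Opening the code to decide whether an adverse event was caused by the drug can tilt the related/unrelated split; relatedness should be recorded masked first

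*Combined protocol and SAP*

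**What the plan says.** The Masking section has a default and one exception. The default is "All masked information will only be opened at the end of the study". The exception, in the same item 5, is "unless an adverse event (AE) requires unmasking to determine whether the AE was due to the treatment medication". Item 1 masks the participants, and item 4 covers the examiner: "The principal investigator is masked from tests and placebo formulation during the follow up dry eye evaluations on subjects".

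The first entry under Safety measures is "Adverse events (treatment related and treatment unrelated". The safety hypothesis, under Clinical hypothesis, is "Natesto has an acceptable safety profile in ocular structures and general systemic system", with no contrast between arms. The Research Rationale calls the trial a "prospective randomized, controlled double masked study".

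The available text does not say who judges relatedness, whether that judgement is recorded before the code is opened, who learns the assignment, or how often an event would need unmasking. The section on general statistical methods gives no analysis of adverse events. Part of the text after the Confidentiality heading was not in the copy reviewed, so any adverse-event procedure placed there could not be checked.

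**The concern.** Relatedness is itself an outcome of this trial. Item 5 makes settling it the reason to look up the allocation, so for those events an outcome is decided with the arm in view. Opening the code helps settle causality only if a placebo assignment counts against relatedness or an active assignment counts for it. Two identical events can then be classified differently because of the arm, and the difference runs one way: more related events on active, fewer on placebo.

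This is a live question here. Both arms receive the same vehicle, including castor oil, so a local eyelid reaction can occur in either. The protocol's background section says it is unknown whether virilization effects will occur in women. At stake is the credibility of the related/unrelated table, which is the only way of summarising adverse events that the available text defines.

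**Working it through.** **The plan's own figures.** No document figure covers adverse-event rates or unmasking. The nearest design figure is the power in Table 2: 17 per arm, difference 2.5 s, SD 2.5 s, two-sided 0.05. The noncentral t with 32 degrees of freedom gives 0.807037, as printed. It does not bear on this point and the fix does not alter it.

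**Reading the text.**
1. Item 5 gives a purpose for the early break, and that purpose is causality.
2. Safety measures make causality an outcome.
3. No available text places a masked judgement before the break.
4. So for each event unmasked under item 5, that outcome is settled with knowledge of the arm.
5. Item 5 is an exception, so events not unmasked are still classified masked.
6. Total adverse events, visual acuity, biomicroscopy, ophthalmoscopy, IOP and hair evaluation do not use relatedness and are not touched.

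**Illustration (every rate here is assumed).** Let *a* be the risk of an adverse event, equal in both arms; *u* the share of events unmasked, equal in both arms; *m* = 0.50 the probability of being called related when judged masked; *r*A = 0.80 and *r*P = 0 the same probabilities on active and placebo when judged unmasked. Each subject counts once.

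- Related on active = a[(1 − u)m + u·rA]
- Related on placebo = a[(1 − u)m + u·rP]
- False difference = a·u·(rA − rP) = 0.80·a·u

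Example, a = 0.40 and u = 0.25: active 0.40 × (0.375 + 0.20) = 0.230; placebo 0.40 × 0.375 = 0.150; difference 0.080.

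False excess of related events on active, in percentage points:

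| Event risk | 10% unmasked | 25% | 50% | 100% |
|---|---|---|---|---|
| 20% | 1.6 | 4 | 8 | 16 |
| 40% | 3.2 | 8 | 16 | 32 |
| 60% | 4.8 | 12 | 24 | 48 |

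If someone applied Fisher's exact test at 0.05 to related events with 17 per arm (a test that the plan does not specify), the chance of rejection with no true difference would be:

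| Event risk | None unmasked | 10% | 25% | 50% | 100% |
|---|---|---|---|---|---|
| 20% | 0.008 | 0.008 | 0.012 | 0.027 | 0.122 |
| 40% | 0.019 | 0.022 | 0.040 | 0.123 | 0.678 |
| 60% | 0.020 | 0.025 | 0.059 | 0.222 | 0.964 |

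For all events regardless of relatedness it stays at 0.019, 0.022 and 0.022 for the three risks, whatever share is unmasked.

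**Sensitivity to rP.** If vehicle reactions on placebo are still called related, rP is above 0. With rP = 0.40 the 8-point figure halves: 0.40 × 0.25 × (0.80 − 0.40) = 0.040. With rP = rA it is zero.

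**The case against.** The best defence is that item 5 is narrow. The code stays closed unless an event requires unmasking, and that may be rare. No test of related events between arms is planned, and the safety hypothesis asks only for an acceptable profile. All of this stands and limits the size of the point. It does not remove it, because the rule still directs an outcome to be settled by looking at the arm.

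A second objection also stands in part. Item 5 does not define its term for the study medication, and the placebo shares the vehicle, so a placebo reaction could still be called related. The bias is therefore possible and not automatic, as the sensitivity step shows.

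Four stronger readings are tempting and are not supported:

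- A reader might infer that the whole related/unrelated classification is made knowing the arm. Item 5 reaches only the events unmasked under it.
- A reader might infer that the safety comparison as a whole is biased. Only the relatedness split depends on attribution.
- A reader might infer that the co-primary outcomes, breakup time and secretion grade, are graded by an unmasked examiner. That depends on who learns the arm, which the available text does not say. Item 4 masks the principal investigator at follow-up without exception, and an unmasked assistant already implements the randomization.
- A reader might turn the oily-skin (20%) and acne (4%) rates in the background section into a number of subjects unmasked. Those are event rates in androgen-deficient subjects dosed through abdominal skin. They are not eyelid data or unmasking frequencies, and the documents give no placebo rate beside them.

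**Conclusion.** The concern holds as a limited risk. Item 5 permits the code to be opened to decide causality, and no available text requires a masked judgement first. For events handled this way, the related/unrelated split can be biased toward more related events on active.

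The actual size cannot be derived from the documents. On the assumed rates above, the false excess runs from 1.6 points (20% event risk, 10% unmasked) to 48 points (60% risk, all unmasked); it is small if unmasking is rare and shrinks further if placebo events can be called related. The conclusion rests on item 5 being applied as written and on no contrary procedure in the text that could not be seen. It should be corrected because the remedy is simple, but it does not undermine the trial's efficacy analysis or its other safety measures.

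**What to change.** Amend Masking item 5 and the adverse-event reporting as follows:

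1. The masked investigator judges and records relatedness before any code break.
2. The related/unrelated tables use that masked judgement. A later unmasked opinion may be recorded separately but does not replace it.
3. All adverse events are also tabulated by arm regardless of relatedness.
4. Each break is logged with date, reason and who was told.
5. The assignment is not passed to the dry-eye examiner, so that item 4 continues to hold.

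When a subject's care justifies opening the code is a clinical matter, and this point makes no proposal on it.

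The cost is small: revised wording, a relatedness field on the case report form (the readable part of Appendix III shows no adverse-event section) and a break log. The unmasked assistant who could hold the code is already in place. Some relatedness calls will remain at possible until the end of the study. The sample size of 34 and the power of 0.807 are unchanged.
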